Quantifying Patient-Specific Changes in Neuromuscular Control in Cerebral Palsy

NCT #: NCT02699554

Date: 3/15/2022

STUDY PROTOCOL

Background

Current treatments for individuals with cerebral palsy (CP), such as orthopaedic surgery, fail to make significant improvements in gait for 50% of treated patients. CP is caused by an injury to the brain near the time of birth; however, quantifying how this injury contributes to impaired movement remains challenging. We theorize that patient-specific differences in neuromuscular control contribute to the variable and unsatisfactory outcomes after treatment in CP; quantifying these differences is key to understanding and improving pathologic movement. Recent evidence from human and animal studies suggests that control of movement can be described by muscle synergies; low-dimensional, weighted groups of muscles that are consistently activated together in fixed ratios. Synergies are calculated from electromyography (EMG) using matrix factorization algorithms, such as nonnegative matrix factorization (NNMF). During gait, synergies can describe muscle activity in unimpaired individuals. After stroke, even fewer synergies are required, suggesting simplified control that may contribute to impaired movement. In a study of over 500 individuals with CP, we demonstrated that synergy complexity was also reduced compared to unimpaired individuals. Further, our preliminary results suggest that individuals with complex synergies, more similar to unimpaired individuals, are more likely to have good outcomes after a variety of treatments compared to individuals with reduced synergy complexity.

These results motivate our proposed research to use synergies as a framework to quantify altered neuromuscular control in CP and inform treatment planning. There are several important knowledge gaps that need to be addressed to determine the clinical utility of synergy analyses. First, we need to determine if an individual's synergies predict treatment outcomes and provide additional insight beyond traditional tools of clinical motion analysis. Second, we need to establish the adaptability of synergies. EMG is typically only collected before treatment in clinical motion analysis and we do not know if or how neuromuscular control changes after treatment. If synergies can change, new treatment strategies such as biofeedback training may be able to target altered synergies and improve movement. If synergies do not change, we can use an individual's synergies to predict responses to different treatments and identify their "best" possible gait pattern given their neurologic capacity. Finally, from a theoretical perspective, we need to further develop our understanding of the contribution of altered synergies to impaired movement in CP. We developed a new algorithm in OpenSim, an open-source platform for musculoskeletal modeling, which allows users to specify and test different control strategies. We will use this platform to create patient-specific simulations and evaluate how changes in synergies influence muscle recruitment, movement, and energy costs of walking.

The long-term goals of the proposed research are to improve movement and quality of life for individuals with CP. This proposal will determine if quantifying altered neuromuscular control with synergy analysis and musculoskeletal simulation can provide clinicians with new tools to optimize treatment and improve walking ability. Our specific aims are to:

Aim 1: Determine if pre-operative synergies predict outcomes at 12 months after orthopaedic surgery. We will recruit 55 individuals with diplegic cerebral palsy (CP) who are undergoing single-event multi-level orthopaedic surgery (SEMLS) at Gillette for standard of care. Each individual will receive gait analysis including EMG to evaluate synergies before and after surgery, which is part of standard of care. We hypothesize that individuals with more complex synergies (i.e., synergies similar to unimpaired individuals) will have greater improvements in walking kinematics, energy costs, and quality of life 12 months after orthopaedic surgery.

Aim 2: Evaluate stability of synergies with respect to time and treatment. With the same participants as Aim 1, we will compare synergies during gait between two visits before surgery and 6 and 12 months after surgery. This investigation will determine whether synergies are repeatable between days in CP and whether synergies adapt or change in response to surgical changes to the musculoskeletal system.

Human Subjects Involvement, Characteristics, and Design

Aims 1 and 2 will use the same set of subjects to evaluate if synergies predict outcomes after SEMLS (Aim 1) and if synergies change after surgery (Aim 2). We will recruit 55 individuals with CP who have been recommended for surgical treatment at Gillette Children's Specialty Healthcare over three years. Our inclusion criteria for Aims 1 and 2 are: age > 6, diagnosis of spastic diplegic cerebral palsy, GMFCS Levels I-III, absence of dystonia/ataxia/athetosis, no prior surgical procedures, no pharmacological spasticity treatments (e.g. botulinum toxin, baclofen, etc.) within 3 months prior to first gait analysis, capacity to follow instructions and provide informed assent, ability to walk across 30 ft. walkway at least 10 times, absence of acute or chronic pain in lower-extremities, and no current pharmacological agents that impact neuromuscular control. Subjects will be recruited who are being evaluated for SEMLS surgery and includes one or more of the following procedures: femoral and tibial derotation osteotomies, surgical lengthening of the gastrocnemius, psoas, hamstrings and adductors, bone and soft tissue alignment of the foot, botulinum toxin injection, distal femoral extension osteotomy, and patellar tendon advancement. Subjects will not be excluded on the basis of ethnic background, race, sex, or socioeconomic factors.

Each subject will receive instrumented gait analysis before and after treatment. Post-operative gait analyses will be at 6 and 12 months to ensure that the patients are ambulatory and to evaluate neuromuscular control over a full year of recovery. Each gait analysis will include kinematics, kinetics, electromyography (EMG), and a physical exam. EMG will be collected for 5 muscles on each leg. Subjects will perform a minimum of 5 trials walking across the laboratory at each visit. The physical exam will be completed by an experienced pediatric physical therapist and include evaluations of range of motion, spasticity (Modified Ashworth Score, Tardieu Scale, and instrumented spasticity measurement system), selective motor control (SCALE), manual muscle strength, and bone alignment.

a. Potential risks:

There are minor risks associated with completing motion analysis during gait; however, these risks are not greater than minimal risk and are similar to activities of daily living. Tripping and falling are possibilities and we will take numerous precautions to prevent such risk, as described below. Fatigue and muscle soreness are also potential risks and we will provide adequate time to rest and recover for all tasks.

b. Recruitment and informed consent:

Children with cerebral palsy will be recruited from Gillette Children's Specialty Healthcare using brochures designed to describe the research and involvement. An experienced research coordinator will assist with recruiting and contacting potential participants. Before gait analysis, each subject will receive a thorough explanation of the protocols from a member of the research team. We will obtain informed permission from the parent or guardian and assent from the child.

Children that do not voluntarily communicate their assent and understand the procedures will not be included in the study. Information will be provided verbally and in writing. Subjects will be reassured of their right to withdraw at any time from the study.

c. Protection against risks:

We take numerous precautions to protect against risks associated with using motion capture to analyze human movement. To prevent tripping and falling we ensure that the floor of the lab is free from wires or other obstructions. Additionally, we can provide additional support through harnesses, bracing, or walking beside the subject, if necessary. Electromyography is also safe and has been tested and used extensively during gait and similar tasks. We will inspect all wires and connections before every experiment. Subjects will be given frequent breaks during all experiments to avoid fatigue. For all experiments, subjects can terminate the experiment at any time. To protect against any breach in confidentiality, data collected for this study will be stored securely on password-protected computers. Codes instead of names of subjects will be used on all data files and reports. Any data used for publication or presentations will be de-identified.

d. Potential benefits of the proposed research to human subjects and others:

There are no immediate potential benefits to the participants in this study.

e. Importance of the knowledge to be obtained:

The potential risks associated with this study are reasonable in the context of the knowledge and advancement in our understanding of cerebral palsy that will be gained. We anticipate that the proposed experiments will provide a new framework for quantifying altered neuromuscular control in cerebral palsy and improving treatment planning. This research will provide insight into the impact of orthopaedic surgery and evaluate the potential of using measures of altered neuromuscular control to predict outcomes. The results from this work will also be extendable to other clinical populations such as stroke, traumatic brain injury, spinal cord injury, and multiple sclerosis, which also exhibit impaired neuromuscular control.

STATISTICAL ANALYSIS

Aims 1 and 2 prospectively evaluate neuromuscular control among individuals with cerebral palsy who are receiving single-event multi-level orthopaedic surgery (SEMLS) as part of their standard care at Gillette Children's Specialty Healthcare. Our sample size analysis, based upon our prior analyses of synergy complexity repeatability and associations with outcomes, suggest a sample size of 55 subjects for 90% power to detect $\frac{1}{2}$ a standard deviation change in synergy complexity assuming a 20% drop-out rate, alpha = 0.05. This sample size is based upon Aim 2 to detect if synergies change after treatment. In our preliminary analysis, a $\frac{1}{2}$ standard deviation change in synergy complexity (Dynamic Motor Control, DMC) was associated with a 5-point difference in the Gait Deviation Index (GDI), which is generally the threshold for defining a clinically significant improvement in walking ability in clinical motion analysis. We are evaluating synergy complexity using DMC, which we previously evaluated and tested on over 500 children with cerebral palsy and 84 typically-developing children. In this prior research, DMC could differentiate between functional ability levels among individuals with cerebral palsy.

We use causal modeling and Bayesian Additive Regression Trees (Table 1) to evaluate whether pre-operative synergy complexity and structure are associated with changes in GDI after SEMLS at 12 months post-op. We constructed our causal model with a Directed Acyclic Graph (DAG). The logic behind our DAG is as follows:

1. Our objective was to determine the impact of SEMLS on change in GDI (Δ GDI). Thus, SEMLS is our exposure and Δ GDI is our outcome. SEMLS induces a change in impairments (Δ Imp) that causes the observed Δ GDI.
2. The covariates we identified as common causes of both SEMLS and Δ GDI included: Age, baseline GDI (GDI_{pre}), and baseline impairment (Imp_{pre}). Baseline impairments represent a set of variables collected during clinical gait analysis to evaluate neurologic and orthopedic impairments (Table 1).
3. Surgical treatment history (Hx) is a common cause of baseline impairment (Imp_{pre}) and whether or not SEMLS is recommended.
4. We included a general severity (Sev) measure as an unmeasured factor that impacts baseline impairment (Imp_{pre}) and surgical treatment history (Hx).

From the DAG we determined the adjustment set needed (e.g., regression, BART) to evaluate the total causal effect of SEMLS on Δ GDI. For this DAG, the minimal sufficient adjustment set to estimate the total causal effect of SEMLS on Δ GDI was: Age, GDI_{pre} , and Imp_{pre} . We also determined the adjustment set to evaluate the total causal effect of baseline impairment (Imp_{pre}) on Δ GDI and GDI_{pre} . The minimal sufficient adjustments sets were Age and Hx for Δ GDI and Age for GDI_{pre} . The plausibility of a DAG can be evaluated by identifying conditional independencies, variables that should be independent given the causal relationships defined in the DAG. We identified the adjustment sets and independencies with dagitty⁴ and all analyses were conducted in R (version 4.1.0)⁵.

To assess the total causal effects of SEMLS and baseline impairments (Imp_{pre}) on change in GDI (Δ GDI) we used Bayesian Additive Regression Trees (BART), a machine learning method that uses a boosted ensemble of regression trees for nonparametric function estimation relying on a Bayesian probability model⁶. Like other tree-based regression methods, an advantage of BART is that it can handle nonlinear effects and interactions⁷. For causal modeling, recent work has demonstrated that BART-based models achieve accurate and precise causal predictions^{8,9}. For this analysis, we used BART models to estimate Δ GDI using the adjustment sets identified by the DAG. Thus, to identify the impact of SEMLS on Δ GDI, we included the covariates Age,

GDI_{pre} , and Imp_{pre} . Baseline impairments were not available for all participants. Missing data in Imp_{pre} were imputed using multivariate imputation by chained equations (MICE)¹⁰. We used the *bartMachine* package to implement the analysis¹¹. We optimized the hyperparameters for each BART model using 10-fold cross-validation. We report the pseudo- R^2 ($1 - \text{SSE}/\text{SST}$) for each BART model and used k-fold cross-validation ($k = 10$) to determine the out-of-sample root mean square error (RMSE).

To assess the relative effects of individual variables from BART, we used accumulated local effect (ALE) analysis¹². The ALE analysis is similar to a partial dependence plot, but the averaging is done locally to avoid including observations that are unlikely to ever be realized (e.g., someone walking three standard deviations slower than average but with a normal cadence). The ALE plots illustrate the impact of each variable over the range of values for that variable, conditioned on the other covariates in the model. Thus, ALE plots can be useful for examining nonlinear effects identified by BART. For example, the ALE plot can highlight nonlinear effects such as when a variable impacts GDI with a deviation from average (i.e., a U-shaped plot) or when a variable only impacts GDI above or below a certain cut-off (i.e., a step function or discontinuity).

Table 1: Variable definitions

Variable	Description
GDI	Overall measure of the deviation in an individual's kinematics compared to nondisabled peers scaled such that mean(sd) over the nondisabled population is 100(10) ¹³ . Kinematics were evaluated using marker-based motion analysis and a modified plug-in-gait marker set.
SEMLS	Binary variable indicating whether or not child had single-event multi-level orthopedic surgery, defined as a surgery with two or more orthopedic surgeries on at least one leg.
Hx	Binary list of prior surgical treatments.
Age	Years from birth defined as days/365.25
Impairments	Spasticity: Mean modified Ashworth score across plantarflexors, hamstrings, hip adductors, and rectus femoris.
	Strength: Mean manual muscle strength score across hip flexors/extensors, knee flexors/extensors, and ankle dorsiflexors/plantarflexors where 1 is defined as a 'visible or palpable contraction' and 5 is defined as 'full range of motion against gravity'.
	Static Motor Control (SMC): Mean static motor control score across hip abduction, hip flexion, hip extension, knee extension, and ankle plantarflexion where 0 is very little or no control of single joint movement, 1 is impaired voluntary movement at a single joint, and 2 is good voluntary movement at a joint.
	Dynamic Motor Control (DMC): Measure of the complexity of muscle activity during gait evaluated from synergy analysis of EMG data. Complexity is evaluated as the total variance accounted for by one synergy of EMG data during CGA and compared to nondisabled peers scaled such that mean(sd) over the nondisabled population is 100(10) ^{14,15} .

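### The SAP plans a causal effect of SEMLS in a cohort described as all receiving SEMLS, and names no DMC-specific estimand for Aim 1

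*Combined protocol and SAP*

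**What the plan says.** **Exposure.** The STATISTICAL ANALYSIS section introduces the causal model as a way to relate pre-operative synergy complexity to GDI change 12 months after SEMLS. DAG item 1 then reads "Our objective was to determine the impact of SEMLS on change in GDI" and makes SEMLS the exposure. The adjustment-set paragraph plans its total causal effect on GDI change, adjusting for Age, baseline GDI (GDI_pre) and baseline impairment (Imp_pre). Table 1 makes SEMLS binary and requires at least two orthopaedic procedures on one leg.

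**Cohort.** The Aim 1 paragraph says "We will recruit 55 individuals with diplegic cerebral palsy (CP) who are undergoing single-event multi-level orthopaedic surgery (SEMLS"). The statistical section says "individuals with cerebral palsy who are receiving single-event multi-level orthopaedic surgery (SEMLS) as part of their standard care". Human Subjects Involvement, Characteristics, and Design enrols children "who have been recommended for surgical treatment at Gillette", and adds "Subjects will be recruited who are being evaluated for SEMLS surgery and includes one or more of the following procedures". It also requires "no prior surgical procedures", whereas the DAG and Table 1 use Hx, a list of earlier surgical treatments.

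**Follow-up.** "Each subject will receive instrumented gait analysis before and after treatment", and "Post-operative gait analyses will be at 6 and 12 months".

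**DMC.** Table 1 places DMC among the impairments that make up Imp_pre. The SAP names a total causal effect of Imp_pre on GDI change, with Age and Hx as the adjustment set, and plans accumulated local effect (ALE) curves for individual variables.

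**The concern.** A yes/no exposure needs children on both sides. If every analysed child had SEMLS, the data cannot separate the effect of surgery from everything else that happens over the year, and no modelling method changes that. A model fitted anyway could be reported as a causal surgical effect that the cohort does not support.

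Aim 1 asks about something else, namely whether pre-operative synergies predict outcome. The exposure for that question is DMC, which the SAP treats only as one member of a block. Two models for GDI change are planned with different covariates, and an ALE curve is conditional on whatever else is in its model. The DMC curve reported for Aim 1 could therefore come from either model and carry either meaning.

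**Working it through.** **1. The plan's own number.** Inputs from the sample-size paragraph: a change of half an SD in DMC, 90% power, alpha 0.05, 20% drop-out. A two-sided paired t test (sidedness is not stated; two-sided reproduces the figure) needs n = 44, with power 0.9000; n = 43 gives 0.893. Then 44 / 0.80 = 55, an exact match. The plan states that this size rests on Aim 2, so it was not chosen for a SEMLS contrast. The expected number analysed is 55 x 0.8 = 44.

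**2. All 44 had SEMLS.** The SEMLS column equals the intercept column. A linear design with an intercept, SEMLS and three covariates has 5 columns but rank 4, so the SEMLS effect is not identified. This needs no assumed value.

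**3. A few children are coded 0.** The recruitment wording allows children still under evaluation and a single listed procedure; Table 1 needs two or more on one leg. A child coded 0 through that gap had either a smaller operation or none. A child with no operation has no follow-up visit in the schedule, which is set post-operatively.

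The documents give neither the number of such children (n0) nor the SD of GDI change, so both are assumed. Take n0 from 1 to 22 and SD 7, 10 or 13 points. The difference to detect is 5 GDI points, the plan's threshold. The comparison is an unadjusted two-sample t test with 42 degrees of freedom:

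- SE = SD x sqrt(1/n0 + 1/(44 - n0))
- 95% half-width = t(0.975, 42) x SE = 2.018 x SE
- power from the noncentral t distribution with noncentrality 5/SE

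Example, SD 10: n0 = 1 gives SE = 10 x sqrt(1 + 1/43) = 10.12 and half-width 20.4; n0 = 4 gives SE = 10 x sqrt(1/4 + 1/40) = 5.24 and half-width 10.6.

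| n0 of 44 | Half-width, SD 7 / 10 / 13 (points) | Power for 5 points, SD 7 / 10 / 13 |
|---|---|---|
| 1 | 14.3 / 20.4 / 26.5 | 10.6% / 7.7% / 6.6% |
| 2 | 10.2 / 14.6 / 19.0 | 16.1% / 10.4% / 8.1% |
| 4 | 7.4 / 10.6 / 13.8 | 26.5% / 15.4% / 11.1% |
| 11 | 4.9 / 7.0 / 9.1 | 51.8% / 28.9% / 19.1% |
| 22 | 4.3 / 6.1 / 7.9 | 63.9% / 36.7% / 23.8% |

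These figures illustrate precision. They do not reproduce the BART analysis.

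**4. Which curve answers Aim 1.** The first model for GDI change holds SEMLS, Age, GDI_pre and Imp_pre. The second holds Imp_pre, Age and Hx. Among recipients with no earlier surgery, SEMLS and Hx are both constant. The first then reduces to Age, GDI_pre and Imp_pre, and the second to Age and Imp_pre, so they differ only in GDI_pre. The SAP itself treats GDI_pre as an outcome of Imp_pre, so the choice changes what the DMC curve means. In addition, DMC is one of several impairments, and the SAP does not say whether its effect is to be read with the others held fixed.

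**The case against.** **The analysed data may be wider than the 55 recipients.** Table 1 records whether or not SEMLS took place, DAG item 3 refers to whether it is recommended, and Hx would be pointless if nobody had earlier surgery. This stands. A reader might infer that the SEMLS effect simply cannot be estimated; the documents do not support that without qualification, because they do not settle which children are analysed. They also describe no wider dataset, so the conflict remains.

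**An estimand containing DMC is named.** This stands too. A reader might infer that Aim 1 has no estimand at all, but the SAP gives a total effect of Imp_pre with its own adjustment set, plans ALE curves, and states the outcome and the 12-month time point. What is missing is the DMC-specific part: the contrast, the treatment of the other impairments, and the model whose curve counts.

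**A comparator need not be untreated.** Correct. Table 1 contrasts SEMLS with not-SEMLS and claims nothing more. The objection to a group coded 0 is that it is unplanned and undescribed.

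**The precision figures are assumed and unadjusted.** Also correct. With 11 children coded 0 and SD 7 the half-width is 4.9, just inside 5 points, and useful covariates would narrow it. Imprecision is clear for small n0 but not in every case.

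**The Age and Hx set.** A reader might infer that this set is wrong among recipients, because restricting to them could open a path through GDI_pre. The size of any such bias would rest wholly on coefficients that the documents do not give, and adding GDI_pre would replace the planned total effect with a different quantity. The documents do not show that the set must be changed. They show that the choice has to be stated.

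**Conclusion.** The concern holds as an inconsistency between the stated exposure and the stated cohort, and confidence in that is high. Read literally, the SEMLS effect is not identified. If 1 to 4 of 44 children fall outside the Table 1 definition, the 95% half-width is about 20 to 11 points at SD 10 (7.4 to 26.5 over SD 7 to 13), against a threshold of 5. That range rests on the assumed SD, the assumed counts and an unadjusted comparison; the constant-exposure case rests on none of them. If a wider dataset is meant, the defect is that it is not described.

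This is a should-fix. The SEMLS effect is neither Aim 1 nor Aim 2, the Aim 2 sample size reproduces exactly, and a DMC result can still be produced from the planned models once one of them is named.

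**What to change.** First reconcile the Aim 1 paragraph, the Human Subjects section, the opening of STATISTICAL ANALYSIS and Table 1 on two points: which children are analysed, and who counts as having SEMLS. Settle the conflict between Hx and the exclusion of earlier surgery at the same time.

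**If the analysed cohort is the SEMLS recipients:**

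- withdraw the causal effect of SEMLS;
- restate DAG item 1 with pre-operative DMC as exposure and 12-month GDI change as outcome;
- drop Hx if it is constant;
- name one model's DMC ALE curve as the Aim 1 result, list its covariates, and say whether it is read as a total effect, a direct effect or a conditional association.

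The SAP describes its analyses in the past tense. If they have already been run, disclose that this choice is post hoc.

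**If a wider dataset with children not having SEMLS is intended:** state its source, eligibility, size and interval between visits, and limit the SEMLS estimate to the range of covariate overlap.

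**Cost.** The first route changes SAP wording, plus the post hoc disclosure if it applies, and needs no new data; the sponsor gives up the SEMLS causal claim for this cohort. The second route needs a comparator group to be sourced and described, from existing records or further data.

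### Must the Aim 1 analysis of pre-operative DMC adjust for baseline GDI because only operated children are studied?

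*Combined protocol and SAP*

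**What the plan says.** All places are in the combined protocol and SAP.

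- **Question.** The Statistical Analysis section sets out to evaluate "whether pre-operative synergy complexity and structure are associated with changes in GDI after SEMLS at 12 months post-op". Aim 1 is worded as prediction of outcome, and its hypothesis is that children with more complex synergies "will have greater improvements in walking kinematics, energy costs, and quality of life 12 months after orthopaedic surgery".
- **Causal graph.** Age, baseline GDI and baseline impairment each cause both SEMLS and ΔGDI. Prior surgery (Hx) causes baseline impairment and SEMLS. Unmeasured severity causes baseline impairment and Hx. Table 1 lists DMC among the impairments.
- **Adjustment sets.** For SEMLS the set is Age, baseline GDI and baseline impairment. For baseline impairment: "The minimal sufficient adjustments sets were Age and Hx for Δ GDI".
- **Models.** Bayesian Additive Regression Trees (BART) are used "To assess the total causal effects of SEMLS and baseline impairments (Imp_{pre}) on change in GDI", with the sets taken from the graph. Covariates are then written out for one model only: "Thus, to identify the impact of SEMLS on Δ GDI, we included the covariates Age", followed by baseline GDI and baseline impairment.
- **ALE plots.** Each variable's curve is conditioned on the other covariates in the model, but the model is not named.
- **Population.** The section describes children receiving SEMLS, while Table 1 codes SEMLS as yes or no. The eligibility criteria require no previous surgery.

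**The concern.** If the DMC curve is drawn from operated children only, SEMLS is held fixed. In the plan's graph SEMLS is a common effect of baseline impairment and baseline GDI, so fixing it links the two. The path impairment → SEMLS ← baseline GDI → ΔGDI is then open given Age and Hx, and adding baseline GDI closes it. A causal reading of the DMC curve could therefore carry a selection effect.

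The two planned ΔGDI models also answer different questions. Without baseline GDI, the DMC curve includes whatever runs through baseline gait. With it, the curve compares children who start from the same gait. The Background hopes that synergies "predict treatment outcomes and provide additional insight beyond traditional tools of clinical motion analysis", which points to the second model; the BART paragraph's total effect points to the first. Since the ALE paragraph names neither, a reader shown one unlabelled curve could not tell whether DMC adds to baseline gait, and the choice might be made after both had been seen.

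**Working it through.** **1. The plan's own figures reproduce.** A two-sided paired t-test at 0.05 with a 0.5 SD change and 90% power needs 44 children, and 44/(1 − 0.20) = 55, the stated sample size. The point at issue does not touch it.

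The graph was rebuilt from the four numbered rules, plus baseline impairment → baseline GDI (implied because the plan estimates that effect). Eight optional edges not stated in words were switched on or off, giving 2^8 = 256 versions. Twelve reproduce all three stated adjustment sets. In all twelve, Age and Hx form the only minimal set for the total effect of impairment on ΔGDI with SEMLS left free. The stated set is right for the stated effect.

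**2. Operated children only.** In all twelve versions, conditioning on SEMLS leaves the path open given Age and Hx, and adding baseline GDI closes it. With no previous surgery Hx is constant, so Age alone remains and the path stays open. The structural point is correct.

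**3. Size of the selection shift.** The documents give no slopes, so every input is an assumption:
- a linear stand-in for BART, in GDI points per half SD of DMC;
- residual SD 8 for baseline GDI and for ΔGDI;
- DMC slope 2.5 at fixed baseline;
- one other impairment, correlated r = 0.3 to 0.7 with DMC and equally related to baseline GDI;
- slope b of ΔGDI on baseline GDI from −0.25 to −0.75;
- half the children operated, log-odds of SEMLS −1 per SD of baseline GDI and −1, 0 or +1 per SD of DMC.

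| Marginal slope of baseline GDI on DMC | Shift without baseline GDI |
|---|---|
| 0 | 0.12 to 0.47, either sign |
| 2.5 | −0.32 to +0.48 |
| 5 | −0.19 to +0.38 |

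The first row is for DMC log-odds of −1 or +1. The largest shift is 0.48/5 = 9.6% of the plan's 5-point threshold. With log-odds of −0.5 per SD of baseline GDI, the largest is 0.30.

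For comparison, the standard error of the DMC slope with 44 completers, ignoring selection, is 8√(1 + b²) / (√44 × 2√(1 − r²)):
- b = −0.25, r = 0.3: 8.246/(6.633 × 1.908) = 0.65
- b = −0.75, r = 0.7: 10/(6.633 × 1.428) = 1.06

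The shift is below one standard error throughout.

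**4. Gap between the two questions.** The partial slope of baseline GDI on DMC is k = marginal slope/(1 + r): 1.47 to 1.92 for a marginal slope of 2.5, and 2.94 to 3.85 for 5. The gap is k × b:
- marginal slope 2.5: 1.47 × (−0.25) = −0.37 to 1.92 × (−0.75) = −1.44
- marginal slope 5: −0.74 to −2.88

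This is the part that runs through baseline gait, a difference in what is estimated and not a bias.

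**5. What adjustment costs.** Baseline GDI enters both the covariate and ΔGDI, so its measurement error (SD e, v = e²) biases the adjusted DMC slope by (1 + b) × k × v/(64 + v). With e = 3 to 5, v/(64 + v) is 9/73 = 0.123 to 25/89 = 0.281:
- marginal slope 2.5: +0.05 to +0.41
- marginal slope 5: +0.09 to +0.81
- b = 0: up to 3.85 × 0.281 = +1.08, while the unadjusted model has no selection shift

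Across the simulated settings with e = 5, this error exceeded the selection shift it was meant to remove in 50% of settings at marginal slope 2.5 and 83% at slope 5. Where DMC is unrelated to baseline GDI the comparison mostly favours adjustment: residual error reached ±0.15, against shifts of 0.12 to 0.47.

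**The case for a change.** The strongest case for a change concerns the estimand more than selection. The two DMC slopes can differ by up to 2.88 points per half SD, more than half of the 5-point threshold (2.88/5 = 58%). The Background's wish for information beyond motion analysis fits the adjusted model, because GDI is itself a summary of kinematics. Two labelled curves would cost little, as both covariate sets are already in the plan.

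Selection can also look large in relative terms. Under a second set of assumed coefficients, with strong selection and a true total effect of 0.050, operated children adjusted for Age and Hx gave 0.171.

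Part of this stands. The ALE paragraph does not name its model, and a DMC curve needs a label saying whether baseline GDI was held fixed. A causal claim from operated children alone also deserves a caveat, above all if the effect is near zero.

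The rest does not require a change. The Background sentence states a knowledge gap, whereas the BART paragraph commits to total effects and the set for impairments is given. The 2.88 separates two legitimate questions. The selection argument needs a population restricted to SEMLS = 1, which the documents do not fix: a SEMLS effect cannot be estimated unless SEMLS varies. The section is also written as work already done, so asking for a choice before results are read may no longer be possible.

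**Conclusion.** No change to the plan follows. The set of Age and Hx is correct under the plan's graph for the total effect the plan names, with SEMLS left free. Restricting to operated children opens a selection path for a causal reading. For prediction or association, which is how Aim 1 is worded, having had surgery simply defines the target population.

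The selection shift is about −0.47 to +0.48 GDI points per half SD of DMC, of unknown sign. It rests entirely on assumed slopes, residual SDs and selection strengths in a linear model, not on anything the documents report. Adding baseline GDI would not recover the total effect. It conditions on a mediator and removes the shift fully only if baseline GDI is measured without error. That is a trade-off with no demonstrated gain.

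The remaining gap is one that analysts fill sensibly when reporting: stating which BART model, which children and which effect the DMC curve represents.
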